8.2 Secondary Efficacy Analysis

Summary tables will be produced by treatment for \log_{10}/cm^2 baseline skin flora, \log_{10}/cm^2 recovery of skin flora, and \log_{10}/cm^2 reduction of skin flora relative to Treatment Day baseline \log_{10}/cm^2 on the inguinal region at 10 minutes and 6 hours following application of the study materials. The tables will include number, mean, standard deviation, minimum and maximum.

CDT

9. SAFETY ANALYSIS

Adverse events and skin irritation scores will be summarized by treatment.

9.1 Adverse Events

All adverse events (AEs) occurring after initiation of study treatment (treatment emergent AEs) will be summarized by severity, relatedness, overall and by treatment group. AEs occurring during the screening period will be summarized separately. All AEs will be classified using the MedDRA dictionary.

All verbatim descriptions will be listed for all AEs, along with information regarding onset, duration, severity, relationship to treatment, and action taken.

Serious adverse events will be summarized and presented according to nature, time to onset, duration, relationship to treatment and outcome.

A Fisher's Exact test will be carried out to compare each safety parameter between the treatment groups.

9.2 Other Safety Variables

Skin irritation scores will be summarized by treatment.

CDT

APPENDIX

LIST OF ABBREVIATIONS AND DEFINITIONS

AE	Adverse event
ATE	Average Treatment Effect
CFU	Colony forming units
CHG	Chlorhexidine gluconate
CRO	Contract Research Organization
DCS	Data Collection Sheet
eCRF	Electronic Case Report Form
EDC	Electronic data capture
FM	Final Monograph
IPA	Isopropyl alcohol
ITT	Intent to Treat
MITT	Modified Intent to Treat
PP	Per Protocol

Revision History

Revision Details:

1 To establish statistical analysis plan before study enrollment.

## 1. BACKGROUND INFORMATION

### 1.1 Name, Description and Intended Use of the Investigational Product

3M™ SoluPrep™ Film-Forming Sterile Surgical Solution (SoluPrep Film-Forming Solution), an FDA-approved over-the-counter (OTC) drug product (NDA 208288), is an antimicrobial skin preparation containing the active ingredients 2% w/v chlorhexidine gluconate (CHG) and 70% v/v isopropyl alcohol (IPA) in combination with inactive ingredients: iso-octyl acrylate/methyl methacrylate/n-vinylpyrrolidone (IOA/MMA/NVP) polymer, acetyltributyl citrate (ATBC), trisodium hydroxylethyl ethylenediamine triacetic acid (HEDTA) and purified water (water). When the solution is applied to the skin, it dries to form a film. The potential benefits of this product, as compared with currently marketed CHG/IPA containing products without a polymer, include improved adhesion of incise drapes to prepped skin. In early clinical use situations, the performance of the SoluPrep film-forming polymer did not appropriately adhere to the patient's skin, resulting in flaking or pilling of the polymer film in some cases. 3M is currently evaluating modifications to the quantitative formulation of the inactive ingredients in SoluPrep Film-Forming Solution including removal of the polymer.

3M™ SoluPrep™ Preoperative Skin Preparation (SoluPrep) is an investigational antimicrobial skin preparation containing 2% w/v chlorhexidine gluconate (CHG) and 70% v/v isopropyl alcohol (IPA) without a polymer component. The product will be available in the following configurations: 10.5-mL tinted and colorless, and 26-mL tinted. The 10.5-mL tinted configuration will be evaluated in the current study.

3M™ CHG/IPA Film-Forming Preoperative Skin Preparation (SoluPrep FF) contains 2% w/v CHG and 70% v/v IPA. SoluPrep FF 10.5-mL tinted configuration will be used as the active control.

Sterile 0.9% saline will be used as the negative control.

### 1.2 Summary of Relevant Studies

SoluPrep FF has been evaluated at outside labs in 4 clinical safety studies, 1) cumulative irritation patch test (21 day) with challenge (EM-05-012853), 2) clinical evaluation to assess the phototoxicity potential (EM-05-012952), 3) clinical evaluation of photoallergy potential (EM-05-013062), and 4) evaluation of impurities: human pharmacokinetics maximum usage trial (EM-05-014226). Under the conditions of these trials, the product was considered to be safe and well-tolerated.

Three in vivo pivotal studies (EM-05-012759, EM-05-012760, and EM-05-013260) conducted at outside labs to demonstrate the effectiveness of SoluPrep FF against resident skin flora showed that the product was well tolerated by the study populations.

Skin condition (erythema, edema, rash, dryness, and denudation) was evaluated in 3 clinical studies (EM-05-014626, EM-05-014733, and EM-05-014753) using a modification of the

3M Confidential

Document Name: CLIN-PROT-ICH-US-05-658998

Clinical and Non-Clinical: CLIN-INDEX-3M-SPON-US-05-014624

**[name]**

SoluPrep FF formulation, which included reduction and removal of the polymer. These 3 studies all evaluated drape adhesion to skin. In the first 2 studies, the modified formulations used in combination with a surgical drape were well tolerated by the subject population, with no AEs reported. In the third study (EM-05-014753), 3 AEs were reported. Two of the 3 were mild in severity and the third was considered moderate. All 3 were probably related to the study products.

Refer to the Investigator Brochure (CLIN-INV-BROCH-US-05-171686) for a summary of the studies conducted.

### **1.3 Risk/Benefit Summary**

There are minimal anticipated adverse health risks for the participants of this study. Considerable safety and efficacy data are available for the active ingredients in the investigational product and preclinical safety studies, as described above, have been completed. Application of the study products may cause skin irritation, which may manifest as minor redness, swelling, itching, cracking or peeling. The incidence of irritation is expected to be low, as is the severity of irritation. Individuals with a known history of sensitivity to acrylates, CHG- or alcohol-containing products, medical tapes, metals, natural rubber latex, vinyl, or skin-marking inks, will be excluded from this study.

There are no direct health benefits to subjects who participate in this study.

### **1.4 Good Clinical Practices and Regulatory Requirements**

3M™ SoluPrep™ Preoperative Skin Preparation is an investigational new drug. This study will be conducted in compliance with the protocol, Good Clinical Practice (GCP), and applicable state and federal regulations including 21 CFR 312 (Investigational New Drug Application), 50 (Protection of Human Subjects), 56 (Institutional Review Boards), 54 (Financial Disclosure by Clinical Investigators), and 45 CFR 160 and 164 (Authorization for Use/Disclosure of Protected Health Information).

### **1.5 Study Population**

Healthy male and female volunteers, 18 years of age or older, with no dermatological conditions on the test sites, or known history of sensitivity to acrylates, CHG- or alcohol-containing products, medical tapes, metals, natural rubber latex, vinyl, or skin-marking inks, will be enrolled into this study. A sufficient number of subjects will be enrolled in the screening phase, such that approximately 100 applications of the investigational product (10.5-mL tinted) and the active control (10.5-mL tinted), in addition to approximately 30 applications of the negative control, are evaluable for efficacy on the inguinal region (groin) at completion of the study. In total, 230 evaluable applications of investigational product, active control, and negative control would require 115 test subjects, utilizing both the right and left sides of the inguinal region. With the expectation that 15% of subjects will not meet treatment day baseline requirements, it is anticipated that 135 subjects will need to be treated. Subjects must satisfy all Screening Day and

3M Confidential

Document Name: CLIN-PROT-ICH-US-05-658998

Clinical and Non-Clinical: CLIN-INDEX-3M-SPON-US-05-014624

**[name]**

Treatment Day Inclusion/Exclusion Criteria prior to collection of screening baselines and Treatment Day procedures. If the required numbers of subjects do not qualify from the initial screening group, additional volunteers will be recruited, as needed.

Each subject will be identified by a screening identification number, and a subject treatment number. Subject treatment numbers will not be assigned until a subject has passed the screening criteria, including screening baseline bacterial counts.

Both the right and left sides of the groin must meet the screening baseline requirements stated in the Inclusion Criteria to qualify for treatment.

## **2. STUDY OBJECTIVES**

The primary objective of this study is to evaluate the antimicrobial efficacy of SoluPrep by demonstrating non-inferiority to SoluPrep FF, an FDA-approved active control, with a 0.5 margin ( $\log_{10}$  scale), and demonstrating a superiority margin of  $1.2 \log_{10}/\text{cm}^2$  to saline, the negative control. In addition, both active products should demonstrate persistence of effect where the 6-hour post-treatment measurement is lower than or equal to the baseline measurement for 100% of the subjects.

Safety will also be evaluated based on the incidence of adverse events reported during the study and assessment of skin irritation ratings.

## **3. STUDY DESIGN**

### **3.1 Study Type and Methodology**

This is a randomized, controlled, third-party blind, single-center study in healthy volunteers where each subject receives 2 of the 3 possible study products on the groin. The study staff performing the bacterial enumeration and the statistician performing the analysis will be blinded to the study products.

Table 3.1A provides a summary of the study procedures. A schematic diagram of the study is included in Appendix 14.1.

[name]

**Table 3.1A Study Summary**

Pre-Study Preparation	14-day Pretreatment Phase	Screening Phase	Treatment Day
Staff reviews study protocol	Discuss study procedures including Inclusion/Exclusion Criteria	Complete Inclusion/ Exclusion Criteria form	Assign sequential subject number Complete Inclusion/Exclusion Criteria form
Prepare consent form	Perform the Informed Consent process	Perform visual skin assessment	Perform visual skin assessment
Obtain IRB approval	Assign subject screening number	Collect screening baseline samples from inguinal region	Perform skin irritation rating
Recruit volunteers for Pretreatment Phase	Complete Inclusion/Exclusion Criteria form	Count screening plates, determine which subjects qualify for study	Per randomization, mark test areas, collect baseline samples from inguinal region
Prepare subject personal hygiene kits	Review subject instructions for wash out and dispense subject personal hygiene kit	Contact eligible subjects, schedule Treatment Day (schedule for clipping, if needed)	Apply study products per randomization
	If needed, perform clipping.		Perform skin irritation rating, collect 10-minute ( $\pm$ 30 sec) post-prep samples
			Perform skin irritation rating, collect 6-hour ( $\pm$ 30 min) post-prep samples

### 3.2 Primary and Secondary Endpoints

#### Primary Endpoints:

The primary endpoints include (1) an immediate efficacy endpoint which is defined as the average treatment effect (ATE)  $\log_{10}$  CFU/cm^2 of skin flora on the inguinal region at 10 minutes following application of the study products relative to the treatment day baseline skin flora, and (2) a persistent efficacy endpoint which is a binary endpoint with success/failure, where “success” is defined as  $\log_{10}$  CFU/cm^2 of skin flora on the inguinal region at 6 hours following application of the study products being lower than the treatment day baseline skin flora.

[name]

Secondary Endpoints:

Secondary microbiological endpoints are the  $\log_{10}/\text{cm}^2$  baseline skin flora,  $\log_{10}/\text{cm}^2$  recovery of skin flora, and  $\log_{10}/\text{cm}^2$  reduction of skin flora relative to Treatment Day baseline  $\log_{10}/\text{cm}^2$  on the inguinal region at 10 minutes and 6 hours following application of the study products.

The principal measure of safety will be the incidence of adverse events reported during the study and a summary of the skin irritation rating scores. A skin irritation rating of 3 in any category represents significant irritation and qualifies as an Adverse Event.

### 3.3 Randomization and Blinding

The left and right test areas on the subject's inguinal region will be assigned according to a computer-generated randomization schedule to receive 1 of the 3 study products (see Table 3.4.1A). Randomization will be balanced between left and right sides. There are 3 different combinations of treatments. These are shown below in Table 5.3.3A. To provide an ample number of subjects, the treatment groups will be randomized into 10 blocks of 12-2-2 for each of groups 1 through 3, respectively. Baseline and post-prep samplings will be randomized to sites within each test area. The same test site randomization will be used on each side of a subject's body to reduce the possibility of sampling errors. An example of one of the blocks is shown in Table 3.3.1 below.

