3.2 Randomization

The left and right test areas on the subject's inguinal region will be assigned according to a computer-generated randomization schedule where each will receive 1 of the 3 study products (see Table 1). Treatment randomization will be balanced between left and right sides. There are 3 different possible combinations of treatments. These are shown below in Table 2.

To provide enough subjects to meet study objectives, the treatment combinations will be randomized in a 6:1:1 ratio for combinations 1 through 3, respectively, at the single recruiting clinical facility. The details of block size will be documented in the final study report.

Baseline and post-prep samplings at 10 minutes and 6 hours will be randomized to three sites within each test area. The same test site randomization will be used on the left and right sides of a subject's body to reduce the possibility of sampling errors.

The Investigator is responsible for ensuring that the study randomization is followed. Randomization envelopes will be provided to the study site.

CDT

Table 1 Study Products

Treatment Code	Study Product	Description
SP	SoluPrep	Contains 2% w/v chlorhexidine gluconate (CHG) and 70% v/v isopropyl alcohol (IPA). 10.5-mL applicator, tinted.
SPFF	SoluPrep FF	Contains 2% w/v chlorhexidine gluconate (CHG) and 70% v/v isopropyl alcohol (IPA) in combination with an acrylate copolymer. 10.5-mL applicator, tinted.
S	Saline	Negative control. Sterile 0.9% saline. 20-mL bottle.

Table 2 Subject Treatments

Treatment Combination	Left and Right Treatment
1	SoluPrep 10.5-mL and SoluPrep FF 10.5-mL (SP + SPFF)
2	SoluPrep 10.5-mL and saline (SP + S)
3	SoluPrep FF 10.5-mL and saline (SPFF + S)

Randomization Plan:

A 3M statistician not assigned to the project will develop a randomization program and generate the randomization code list. The code list will include randomization number, left side treatment, right side treatment, baseline sample site, 10-minute sample site and 6-hour sample site. The randomization assignments will be printed and inserted into security envelopes then tightly sealed.

The Data Manager will strip the treatment assignment from the programs that are used to download the data from Clindex®. This will keep the statistician assigned to the study blinded until data lock.

CDT

Randomization Process:

For each eligible subject to be randomized, the investigator or designee will do the following:

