**Table 3.4.1 Example Randomization**

Random -ization Number	Treatment Group	Left Groin Treatment	Right Groin Treatment	Sampling Site		
				Baseline	10 Minute	6 Hour
1	1	SoluPrep FF	SoluPrep	4	2	3
2	1	SoluPrep FF	SoluPrep	3	2	4
3	1	SoluPrep	SoluPrep FF	4	2	3
4	1	SoluPrep FF	SoluPrep	3	2	4
5	1	SoluPrep	SoluPrep FF	3	4	2
6	3	Saline	SoluPrep FF	4	3	2
7	1	SoluPrep FF	SoluPrep	3	4	2
8	2	SoluPrep	Saline	2	3	4
9	1	SoluPrep FF	SoluPrep	3	4	2
10	1	SoluPrep	SoluPrep FF	4	2	3
11	1	SoluPrep	SoluPrep FF	2	4	3
12	1	SoluPrep	SoluPrep FF	3	4	2
13	3	SoluPrep FF	Saline	4	3	2

3M Confidential

Document Name: CLIN-PROT-ICH-US-05-658998

Clinical and Non-Clinical: CLIN-INDEX-3M-SPON-US-05-014624

[name]

Random -ization Number	Treatment Group	Left Groin Treatment	Right Groin Treatment	Sampling Site		
				Baseline	10 Minute	6 Hour
14	1	SoluPrep	SoluPrep FF	4	3	2
15	1	SoluPrep FF	SoluPrep	3	2	4
16	2	Saline	SoluPrep	3	4	2

The Investigator is responsible for ensuring that the study randomization is followed. Randomization envelopes will be provided to the study site.

The study products cannot be blinded from the Investigator or study staff performing the product application, sample collection and skin assessment due to the obvious differences in applicator design, color, and other physical characteristics. However, the study staff performing the bacterial enumeration will not be involved in the study product application or the collection of samples and, therefore, will be blinded to the study products. The statistician performing the analysis will also be blinded.

Randomization Plan:

A 3M statistician not assigned to the project will develop a randomization program and generate the randomization code list. The code list will include randomization number, treatment group, left side treatment, right side treatment, baseline sample site, 10-minute sample site and 6-hour sample site. The randomization assignments will be printed and inserted into security envelopes then tightly sealed.

The Clinical Data Analyst will remove the treatment assignment from the programs that are used to download the data from Clindex®. This will keep the statisticians and programmers assigned to the study blinded until data lock.

Randomization Process:

For each eligible subject to be randomized, the investigator or designee will do the following:

- Retrieve a randomization envelope with smallest available randomization envelop number.

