### 3.4.4 Additional Study Supplies

Sponsor will provide the following:

- Study Product Disposition Forms
- Randomization schedule
- Data Collection Sheets (DCSs)
- Study products
- Triacetin (Glyceryl triacetate)

Study site will provide the following:

- Subject Informed Consent / HIPAA Authorization forms, IRB-approved
- Product kits (toiletry items to be used by subjects during study)
- Standard Sampling Solution (SSS), 75mM phosphate buffer (0.04% monobasic potassium phosphate, and 1.01% dibasic sodium phosphate) containing 0.1% Triton® X-100, 0.3% lecithin, 3.0% polyoxyethylene sorbitan monooleate (Tween® 80), and 1.0% Tamol™ SN; pH 7.9  $\pm$  0.1, sterile
- Butterfield's sterile phosphate buffered water (PBW), 312  $\mu$ M KH2PO4, pH 7.2  $\pm$  0.1
- High-purity deionized water, sterile
- Trypticase soy agar containing 0.5% Tween 80 and 0.07% lecithin (TSA+N)
- Disposable undergarments
- Gloves, sterile
- Sterile, non-occlusive dressings (to cover treated test sites)
- Alcohol wipes
- Transfer pipettes, polyethylene, sterile
- Serological pipettes, 1 mL, 2 mL, and 10 mL, sterile
- Pipettor, calibrated to accurately deliver volumes of 0.5 mL, 2.5 mL and 3.0 mL, and sterile tips
- Tubes with sealable caps, polypropylene or glass, sterile
- Petri dishes, 100-mm, sterile
- Surgical clippers with blades
- Sterile marking templates, 1.5" x 5" (for marking test sites)
- Non-toxic marking pen (Sharpie or equivalent), sterile (Note: Do not use markers containing crystal violet)
- Scrub cups (2.20 cm I.D., 3.80 cm^2), sterile
- Teflon or rubber policemen, sterile
- Timers or stopwatches
- Pipette-Aid® or similar apparatus
- Vortex mixer
- Water bath (45  $\pm$  2C°)
- Incubator (30  $\pm$  2C°)

[name]

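### Protocol 3.3 discloses the fixed block makeup to a single unblinded site, so part of the allocation sequence can be predicted, and 3.4.4 leaves unclear whether the site also holds the full schedule

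*Combined protocol and SAP*

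**What the plan says.** **Block structure.** Protocol 3.3 says that "the treatment groups will be randomized into 10 blocks of 12-2-2 for each of groups 1 through 3, respectively" and that "Randomization will be balanced between left and right sides". It adds that "An example of one of the blocks is shown in Table 3.3.1 below". The table that follows (headed 3.4.1, a labelling slip) lists all 16 rows with treatment by side and sampling sites.

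**SAP.** SAP 3.2 says only that "the treatment combinations will be randomized in a 6:1:1 ratio for combinations 1 through 3, respectively" and that "The details of block size will be documented in the final study report".

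**Concealment.** Under protocol 3.3 a statistician not assigned to the project generates the code list. "The randomization assignments will be printed and inserted into security envelopes then tightly sealed", and the site opens the envelopes in number order. The same section says that envelopes are supplied to the site.

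**Who knows what.** Table 3.1A has "Staff reviews study protocol" as a pre-study step. Protocol 3.1 describes a single-center study. Protocol 3.3 says that the investigator and the staff who apply product, take samples and assess skin cannot be blinded.

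**The schedule.** Protocol 3.4.4 includes "Randomization schedule" among the items that the sponsor provides, and does not list envelopes. Sections 5.3.3.1, 5.3.3.2 and 14.7 direct staff to work from the randomization schedule.

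**The concern.** Sealed, sequential envelopes protect against selection only if the next assignment cannot be worked out. With a known fixed block and visible past assignments, the end of each block can be deduced. The SAP's silence on block size gives no protection when the protocol publishes it.

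The contrasts at risk are those with saline, which are primary and use a 1.2 log10 margin. In each block of 16, 4 subjects receive saline and 14 receive SoluPrep, but only 2 receive both, so SoluPrep versus saline rests mostly on different people. The site counts the screening plates and then schedules Treatment Days (Table 3.1A). One exclusion criterion rests on the investigator's opinion (4.2). The investigator or a designee completes the Treatment Day eligibility form (5.3.3) and retrieves the envelope (3.3). Foreknowledge could therefore influence which subject takes which slot. Adjusting for baseline does not remove selection on unmeasured factors.

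**Working it through.** **Inputs.** Block of 16 with 12, 2 and 2 assignments to combinations 1, 2 and 3 (protocol 3.3). Planned subjects: 135 (protocol 1.5), or 135/16 = 8.4 blocks.

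**Consistency check.** 12:2:2 reduces to the SAP's 6:1:1, and 10 × 16 = 160 slots. The example rows tally to 12/2/2. By side they split 6 and 6 for combination 1, and 1 and 1 for each of combinations 2 and 3.

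**Formula.** An assignment is certain when everything left in the block is of one type. One item of type j falls after all items of other types with probability 1/(n − c_j + 1). The expected number of certain assignments per block is therefore the sum of c_j/(n − c_j + 1).

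| What is predicted | Sum | Certain per block | Share of 16 | Of 135 subjects |
|---|---|---|---|---|
| Combination | 12/5 + 2/15 + 2/15 | 2.67 | 16.7% | 22.5 |
| Combination plus side | 2 × 6/11 + 4 × 1/16 | 1.34 | 8.4% | 11.3 |
| Certain to be combination 1 | 12/5 | 2.40 | 15.0% | 20.3 |
| Certain to contain saline (combinations 2 and 3 merged) | 4/13 | 0.31 | 1.9% | 2.6 |

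The side row assumes that every block is balanced like the example. A simulation of 40,000 blocks gave 2.66 and 1.34 for the first two rows.

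The last assignment in a block is always certain. At least the last two are certain in (12 × 11 + 2 × 1 + 2 × 1)/(16 × 15) = 57% of blocks.

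**Best guess over all slots (simulation).** Accuracy for the combination rises from 75% with no block information to about 77%. For combination plus side it rises from 37.5% to about 50%.

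**The schedule in 3.4.4.** If it means the set of envelopes, the figures above apply. If it is a full list that enrolling staff can read, every assignment is knowable. The documents do not say which it is, or who holds it.

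**The case against.** **The exposure is small where it matters.** Of the 2.67 certain slots per block, 2.4 are combination 1, where the two actives are compared within the subject. Knowing that a slot is not saline is weaker information than knowing that it is. This stands.

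**Safeguards exist.** Screening eligibility is determined in the data system from plate counts (5.3.4.2). Inclusion in the efficacy analysis depends on a Treatment Day baseline of 5.00 to 7.50 log10 (8.3). Enumeration is blinded, and the regression adjusts for baseline. These limit the damage but do not conceal the sequence.

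**The saline contrast has slack.** SAP 6.2 assumes a difference of 2.26 and needs 1.62 observed, a gap of 0.64. With 135 × 4/16 = 34 saline subjects, the 2.6 predictable ones would each have to shift by 0.64 × 34/2.6 = 8.4 log10 to account for it. That counts only the saline-certain slots. Suppose the 20.3 combination 1 slots among 135 × 14/16 = 118 SoluPrep sides shift in the opposite direction as well. The required shift is then 0.64/(2.6/34 + 20.3/118) = 2.6 log10 each, still large against the assumed SD of 1.0. On the planning assumptions, selection in the certain slots alone is unlikely to change the conclusion.

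**Stronger readings that a reader might infer, and that the documents do not support:**

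- *The envelopes conceal nothing, or every assignment is known in advance.* Protocol 3.3 says that sealed envelopes go to the site, and 3.4.4 may simply be naming them. The stronger reading needs an open list at the site, which no section states.
- *Predictable sides give away the product before the baseline scrub.* The assignment carries the baseline sampling site as well as the treatments, and baseline samples are taken according to it. It is therefore known by then whatever the block size.
- *One group schedules, assesses and picks the next subject.* The documents name the investigator or a designee. They neither combine nor separate these roles.

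**Conclusion.** The point holds as a modest weakness in concealment. The disclosed block makes about 17% of assignments certain for combination (about 23 of 135 subjects), and about 8% for combination plus side. About 20 of the 135 would be known not to involve saline, and about 2.6 known to involve it.

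These figures assume that someone at the site tracks assignments within fixed blocks of 16. The side figure also assumes that every block is balanced like the example. The resulting bias cannot be computed from the documents. It is probably small and would fall mainly on the saline contrasts. The wording of 3.4.4 is a separate ambiguity to be resolved. The change is worth making because the site does not need the block detail, and lost concealment cannot be restored after enrollment.

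**What to change.** 1. In protocol 3.3, delete the block count, the block makeup and the example block. Keep the 6:1:1 ratio and the side balance, as in the SAP.
2. Have the unassigned statistician mix block sizes, for example 16 and 32, and withhold them from the site until data lock. Deleting the text is not enough, because 6:1:1 with sides balanced within blocks already implies multiples of 16. Both sizes keep the ratio and the balance, and four blocks of 16 plus three of 32 still give 64 + 96 = 160 slots. Even if a block were known to be 32, certainty about the combination would fall to (24/9 + 4/29 + 4/29)/32 = 2.94/32 = 9.2%.
3. In 3.4.4, replace the schedule entry with sealed randomization envelopes. In 5.3.3.1, 5.3.3.2 and 14.7, refer to the opened envelope. State who holds the full code list.

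**Cost.** Protocol wording and a regenerated code list before enrollment. Larger blocks allow slightly more chance imbalance if enrollment stops mid-block.
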